2.2 RECRUITMENT STRATEGIES

Study participants will be recruited from the population of patients screened in the lymphoid malignancies clinic of the National Institutes of Health. These will include both referrals from outside physicians as well as patient self-referrals. This protocol may be abstracted into a plain language announcement posted on NIH websites: <https://ccr.cancer.gov/Lymphoid-Malignancies-Branch> and <https://ClinicalTrials.gov>, on NIH social media platforms, and on the official Lymphoid Malignancy Branch social media accounts.

2.3 SCREENING EVALUATION

2.3.1 Screening activities performed prior to obtaining informed consent

Minimal risk activities that may be performed before the subject has signed a consent include the following:

- Email, written, in person or telephone communications with prospective subjects
- Review of existing medical records to include H&P, laboratory studies, etc.
- Review of existing MRI, x-ray, or CT images
- Review of existing photographs or videos
- Review of existing pathology specimens/reports from a specimen obtained for diagnostic purposes

2.3.2 Screening activities performed after a consent for screening has been signed

The following activities will be performed only after the subject has signed the consent for study 01C0129. Assessments performed at outside facilities or on another NIH protocol within the timeframes below may also be used to determine eligibility once a patient has signed the consent.

Assessments and procedures to confirm study eligibility should be completed within 28 days prior to registration (unless otherwise noted). See also the Study Calendar provided in Section [3.9](#).

2.3.2.1 Clinical Evaluations

- Disease history, including: diagnosis, treatment (e.g., systemic treatments, radiation and surgeries), disease status, and significant prior/ongoing side effects and symptoms
- Complete medical and social history, including: all active conditions considered to be clinically significant by the treating investigator, as well as smoking history
- Physical examination, including: height (screening only), weight, vital signs (i.e., temperature, pulse, respiratory rate, and blood pressure); review of medications and symptoms/side effects; and, assessment of performance status

2.3.2.2 Laboratory Evaluations

NOTE: Results from outside NIH are accepted.

- CBC with differential, platelets and reticulocyte count
- Chemistry panels (as noted) or specific analyte required for eligibility, including: Creatinine (i.e., Acute Care Panel); serum calcium, phosphate, magnesium and albumin (i.e., Mineral Panel); ALT, AST, total bilirubin (i.e., Hepatic Panel, direct bilirubin if indicated); LDH
- Serum Lipase and Amylase
- Coagulation panel, including: PT/INR and a PTT
- Thyroid function tests, including: thyroid stimulating hormone (TSH) with reflex free thyroxine (T4)
- Hepatitis B surface antigen (HBsAg), Hepatitis B core antibody, Hepatitis C antibody (HCVAb) (qualitative), HIV 1/2 antibody (qualitative) and HTLV-1/2 serologies (within 3 months). **NOTE:** For individuals with a positive hepatitis B core antibody, HBV DNA PCR will be performed to screen for subclinical infection; for patients with

positive hepatitis C antibody, HCV PCR will be performed; for patients with positive HIV antibodies, HIV1/2 viral load will be checked.

- Urinalysis (with microscopic examination if abnormal)
- Serum or urine pregnancy test (B-HCG) for individuals of childbearing potential
- Clonal T-cell receptor rearrangement by PCR (peripheral blood and/or tissue), within 3 months prior to enrollment.

2.3.2.3 Imaging Studies

NOTE: Results from outside NIH are accepted. Other body areas may be imaged if clinically indicated.

- CT neck, chest, abdomen and pelvis (CT should be performed with IV contrast, unless patient is allergic or has renal insufficiency; other imaging may be substituted at the discretion of the investigator (such as MRI))
- PET/CT torso (extremities to be included if there is confirmed or suspected disease involvement)
- MRI of brain (only in patients with suspected involvement of CNS)

2.3.2.4 Cardiac Evaluation (within 3 months)

- Electrocardiogram (EKG)
- Transthoracic echocardiogram

2.3.2.5 Pulmonary Evaluation (if indicated)

- Diffusing capacity/alveolar volume (DLCO/VA) forced expiratory volume in 1 second (FEV1) for patients with significant pulmonary or smoking history.

2.3.2.6 Other Procedures

- Pathologic review/confirmation of diagnosis by Laboratory of Pathology, NCI (no time limit). If archival sample is not available or not adequate, a fresh tumor biopsy and/or peripheral blood sample will be obtained.

2.4 PARTICIPANT REGISTRATION AND STATUS UPDATE PROCEDURES

Registration and status updates (e.g., when a participant is taken off protocol therapy and when a participant is taken off-study) will take place per CCR SOP ADCR-2, CCR Participant

Registration & Status Updates found at: [https://nih.sharepoint.com/sites/NCI-CCR-OCD-Communications/SitePages/OEC-Administrative---Clinical-Research-\(ADCR\).aspx?Mode=Edit](https://nih.sharepoint.com/sites/NCI-CCR-OCD-Communications/SitePages/OEC-Administrative---Clinical-Research-(ADCR).aspx?Mode=Edit).

2.5 TREATMENT ASSIGNMENT PROCEDURES

NOTE: For NCI CCR registration and enrollment system purposes only

2.5.1 Cohorts

Number	Name	Description
1	Mature T-cell malignancies: Dose Escalation (Closed: prior to amendment 12/07/2022)	Relapsed/refractory mature T-cell malignancies: (up to 24 evaluable patients; 5 dose levels)

Number	Name	Description
2	Mature T-cell malignancies: Dose Expansion	Relapsed/refractory mature T-cell malignancies (not including CTCL): (up to 6 additional evaluable patients; 9 total evaluable at the MTD)

2.5.2 Arms

Number	Name	Description
1	Experimental Treatment: Dose Escalation (Closed: prior amendment 12/07/2022)	Lenalidomide by oral intake at escalating doses of 5, 10, 15, or 20 mg/day on days -7 to 10 of each 21-day cycle (max 6 cycles) with CC-486 (5-azacitidine) at 300mg/day by oral intake on days 1-10, romidepsin at 12mg/m ² by IV infusion on Day 1 and 10 and dexamethasone at 40mg by oral intake on days 1 and 10 of each cycle, to determine MTD
2	Experimental Treatment: Dose Expansion(Closed: with amendment 12/07/2022)	Lenalidomide by oral intake at 20mg on days 1 to 10 of each 28-day cycle (max 6 cycles) with CC-486 (5-azacitidine) at 300mg/day by oral intake on days 1-10, romidepsin at 12mg/m ² by IV infusion on Day 1 and 10 and dexamethasone at 40mg by oral intake on days 1 and 10 of each cycle
3	Experimental Treatment: Dose Expansion	Lenalidomide by oral intake at 20mg (MTD) on days 1 to 10 of each 28-day cycle (max 6 cycles) with CC-486 (5-azacitidine) at 300mg/day by oral intake on days 1-10, romidepsin at 12mg/m ² by IV infusion on Day 1 and 10 and dexamethasone at 40mg by oral intake on days 1 and 10 of each cycle

2.5.3 Arm Assignment

Subjects in Cohort 1 will be directly assigned to Arm 1. Subjects in Cohort 2 will be directly assigned to Arm 2.

Once Amendment version 12/07/2022 is approved, new participants enrolled to Cohort 2 will be assigned to Arm 3 (without the lenalidomide window).

2.6 BASELINE EVALUATION

The following should be performed within 28 days prior to the first dose of lenalidomide unless otherwise noted; tests performed as part of screening do not need to be repeated if they were performed within the specified window prior to initiating treatment.

2.6.1 Clinical Evaluations

- Medical history (interim)
- Physical examination including weight, vital signs (i.e., temperature, pulse, respiratory rate, and blood pressure); review of concomitant medications and symptoms/side

effects; and assessment of performance status (ECOG performance score, see [Appendix A](#)).

2.6.2 Laboratory Evaluations

NOTE: Results from outside NIH are accepted

- Required within 24 hours prior to prescribing lenalidomide:
 - Serum or urine pregnancy test (B-HCG) for individuals of childbearing potential
- Required within 14 days:
 - Serum or urine pregnancy test (B-HCG) for individuals of childbearing potential (required within 10-14 days of prescribing lenalidomide). Prescriptions must be filled within 7 days as required by Revlimid REMS™.
 - CBC with differential, platelets and reticulocyte count
 - Chemistry panels including: Acute Care (sodium, potassium, chloride, CO₂, glucose, BUN, creatinine), Mineral Panel (serum calcium, phosphate, magnesium and albumin) and Hepatic Panel (alkaline phosphatase, ALT, AST, total and direct bilirubin)
 - Others: LDH, Uric acid, Total protein
 - Coagulation panel, including: PT/INR and aPTT
 - Iron panel (includes: ferritin, transferrin, iron), folate, vitamin B12
 - C-reactive protein (CRP)
 - Serum Lipase and Amylase
 - Urinalysis (with microscopic examination if abnormal)
 - HLA typing (A, B, C, DR, DQ)
- Required within 28 days:
 - Lymphocyte Phenotype: T, B and NK cell subsets
 - Peripheral blood flow cytometry

2.6.3 Imaging Studies

Every participant should have an evaluation of known sites of disease as part of baseline evaluation. **NOTE:** Only results from NIH are accepted

- One or more of the following studies: CT, MRI, FDG-PET and/or clinical photography
- Patients with neurological symptoms or signs should undergo MRI scan* of the brain and lumbar puncture

***NOTE:** The MRIs to be done in this study may involve the use of the contrast agent gadolinium, if clinically indicated. The risks associated with MRIs and contrast are discussed in the consent form.

2.6.3.1 Other Procedures

- Bone marrow biopsy and aspiration to assess lymphoma involvement (within 3 months)

- Selected patients with cutaneous disease (as determined by physician PI or AI) will have clinical photography and dermatology assessment performed to assess their skin disease

2.6.4 Research Correlates

NOTE: See Section 5 for additional information. The following sample types will be collected for correlative research studies:

- Required:
 - Blood samples for lymphocyte subset testing and circulating tumor DNA
 - Blood, buccal swab, or saliva for germline DNA
 - Tumor Tissue (archival or fresh)
- Optional:
 - Blood samples for tissue immune cell subset comparison (as outlined in Section 5.1)
 - Bone marrow biopsy
 - Tumor biopsy is required if archival tissue is not available or adequate; otherwise, this is optional.

3 STUDY IMPLEMENTATION

3.1 STUDY DESIGN

To determine the maximum tolerated dose (MTD), and the safety and toxicity profile of the combination of lenalidomide, CC-486 (5-azacitidine) and romidepsin in patients with refractory/relapsed TCM, a phase 1 open-label, non-randomized, single-center study will be conducted at the NCI. A standard “3 + 3” design will be used to determine the MTD of dose-escalated lenalidomide in combination with fixed doses of CC-486 (5-azacitidine), romidepsin (R) and dexamethasone (D) with an expansion cohort at the MTD.

In patients with relapsed or refractory TCM, lenalidomide will be administered by oral intake in a dose-escalation with a starting dose of 5mg daily, a second dose level of 10mg daily, a third dose level at 15mg daily, and a fourth dose level at 20mg daily on days -7 to day 10 of first cycle (see **Table 1** for additional dose levels and schedules, cycles are 21 days each). After the second cycle, lenalidomide will be given from day 1 to day 10 in each cycle for up to six cycles. CC-486 (5-azacitidine) with a dose of 300mg oral intake daily will be given on day 1 to day 10, romidepsin will be administered at a dose of 12 mg/ m² on days 1 and 10 (±2 days) and dexamethasone will be given on day 1 and 10 (±2 days) of the cycle.

After approval of Amendment 12/07/2022: Participants will receive six cycles (each 28 days in length) of: lenalidomide at the MTD from day 1 to day 10, CC-486 (5-azacitidine) at a dose of 300mg oral intake daily given on day 1 to day 10, romidepsin administered at a dose of 12 mg/ m² on days 1 and 10 (±2 days) and dexamethasone on day 1 and 10 (±2 days) of the cycle.

Treatment will continue for a maximum of 6 cycles or until toxicity (i.e., dose limiting toxicity) as found in Section 3.9 or toxicity requiring discontinuation as defined in Section 3.5) or progressive disease.

The treatment will be repeated for up to 6 cycles. The patients are allowed to proceed to stem cell transplantation (SCT) if eligible during and after the protocol treatment. Patients who undergo SCT before all 6 cycles of protocol treatment are administered will be taken off therapy. All patients who undergo SCT will continue to be followed for survival, but not for toxicity (see Section 3.8)

Cycles 1-6												28
Azacitidine												by mouth once per day
Lenalidomide												by mouth once per day
D												D
R												R

Table 1: Dose level and schedule for lenalidomide, CC-486 (5-azacitidine), romidepsin and dexamethasone

DL	Lenalidomide Day 1 -10 (7 days lead in for 1 st cycle)	CC-486 (5- azacitidine) Day 1 to 10	Romidepsin Day 1 and day 10	Dexamethasone Day 1 and day 10
-2	0 mg	200 mg PO	10 mg/m ² IV	40 mg PO
-1	2.5 mg	200 mg PO	12 mg/m ² IV	40 mg PO
1*	5 mg	300 mg PO	12 mg/m ² IV	40 mg PO
2	10 mg	300 mg PO	12 mg/ m ² IV	40 mg PO
3	15 mg	300 mg PO	12 mg/ m ² IV	40 mg PO
4	20 mg	300 mg PO	12 mg/ m ² IV	40 mg PO
* starting dose level				
As of Amendment 12/07/2022:	Lenalidomide Day 1 to 10	CC-486 (5- azacitidine) Day 1 to 10	Romidepsin Day 1 and day 10	Dexamethasone Day 1 and day 10

DL	Lenalidomide Day 1 -10 (7 days lead in for 1 st cycle)	CC-486 (5- azacitidine) Day 1 to 10	Romidepsin Day 1 and day 10	Dexamethasone Day 1 and day 10
DL				
4 (MTD)	20 mg	300 mg PO	12 mg/ m ² IV	40 mg PO

3.2 DOSE LIMITING TOXICITY

A dose-limiting toxicity (DLT) is defined as: any treatment-emergent and related severe (grade \geq 3) toxicity, i.e., toxicity deemed related to lenalidomide, romidepsin and/or CC-486 (5-azacitidine) by the PI or designee and occurring during the MTD observation time, defined as day -7 until end of cycle 1 (normally day 22). Each patient must receive all doses of the investigational medications during cycle 1 to be considered as successfully completing the DLT evaluation period.

The following toxicities and conditions will be recorded, however they will not be considered to be DLTs:

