
- To determine the safety and toxicity profile and the maximum tolerated dose (MTD) of the four-drug combination of CC-486 (5-azacitidine), romidepsin, lenalidomide and dexamethasone in patients with TCM

Eligibility:

- Refractory/relapsed TCM (excluding in Cutaneous T-Cell Lymphoma) defined as follows:
 - Patients with systemic disease
 - Have received at least one line of prior therapy
 - Must have received brentuximab vedotin if the disease is anaplastic large cell lymphoma or CD30-positive cutaneous T-cell lymphoma
- Age \geq 18 years of age
- ECOG performance status of \leq 2 (or \leq 3 if decrease is due to the disease)
- Histologically or cytologically confirmed relapsed and/or refractory mature TCM
- Adequate organ and marrow function

Design:

- Open-label, single-center, uncontrolled Phase 1 study

- “3 + 3” design will be used to determine the MTD of dose-escalated lenalidomide with fixed dose of romidepsin and CC-486 (5-azacitidine)
- An expansion cohort of 9 patients will be evaluated at the MTD
- Maximum 6 cycles (28-day cycle) of combination therapy
- To explore all dose levels, including further evaluation in a dose expansion cohort, the accrual ceiling will be set at 30 patients

STATEMENT OF COMPLIANCE

The trial will be carried out in accordance with International Council for Harmonisation Good Clinical Practice (ICH GCP) and the following:

- United States (US) Code of Federal Regulations (CFR) applicable to clinical studies (45 CFR Part 46, 21 CFR Part 50, 21 CFR Part 56, 21 CFR Part 312, and/or 21 CFR Part 812)

National Institutes of Health (NIH)-funded investigators and clinical trial site staff who are responsible for the conduct, management, or oversight of NIH-funded clinical trials have completed Human Subjects Protection and ICH GCP Training.

The protocol, informed consent form(s), recruitment materials, and all participant materials will be submitted to the Institutional Review Board (IRB) for review and approval. Approval of both the protocol and the consent form must be obtained before any participant is enrolled. Any amendment to the protocol will require review and approval by the IRB before the changes are implemented to the study. In addition, all changes to the consent form will be IRB-approved; an IRB determination will be made regarding whether a new consent needs to be obtained from participants who provided consent, using a previously approved consent form.

TABLE OF CONTENTS

PRÉCIS	2
STATEMENT OF COMPLIANCE	4

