1 INTRODUCTION

1.1 STUDY OBJECTIVES

1.1.1 Primary Objective

- Determine the safety and toxicity profile and the maximum tolerated dose (MTD) of lenalidomide given as part of a four-drug combination treatment with romidepsin, CC-486 (5-azacitidine) and dexamethasone to patients with mature T-cell malignancies (TCM).

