10.3 POPULATION FOR ANALYSIS

10.3.1 Evaluable for toxicity:

All patients will be evaluable for toxicity from the time of their first treatment with lenalidomide, romidepsin and CC-486 (5-azacitidine).

10.3.2 Evaluable for objective response:

Only those patients who have measurable disease present at baseline, have received at least one cycle of therapy, and have had their disease re-evaluated will be considered evaluable for response. These patients will have their response classified according to the definitions stated above, Section **6.3.** (NOTE: Patients who exhibit objective disease progression prior to the end of Cycle 1 will also be considered evaluable.)

10.3.3 Evaluable Non-Target Disease Response:

Patients who have lesions present at baseline that are evaluable but do not meet the definitions of measurable disease, have received at least one cycle of therapy, and have had their disease re-evaluated will be considered evaluable for non-target disease. The response assessment is based on the presence, absence, or unequivocal progression of the lesions.

10.3.4 Evaluable for DLT:

All participants who either completed cycle 1 treatment or experienced a DLT during cycle 1 will be evaluable for DLT. If a participant did not experience DLT and did not finish cycle 1 treatment, they will not be evaluable for toxicity and will be replaced in the dose level.

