10.4.2 Analysis of the Primary Endpoints

Safety summaries will include summaries in the form of tables and listings. Reports will include the frequency (number and percentage) of treatment emergent AEs grouped by severity of the AE (per CTCAE, v5.0) and by relationship to study drug (e.g., lenalidomide, romidepsin, CC-486 (5-azacitidine) in any combinations).

Laboratory shift tables containing counts and percentages will be prepared by treatment assignment, laboratory parameter, and time. Summary tables will be prepared for each laboratory parameter. Figures of changes in laboratory parameters over time will be generated.

Results of vital sign assessments, ECGs, and physical exams will be tabulated and summarized.

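### The DLT definition leaves out toxicity attributed to dexamethasone alone, which conflicts with the four-drug primary objective and with Table 6

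*Combined protocol and SAP*

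**What the plan says.** The précis sets out to determine "the maximum tolerated dose (MTD) of the four-drug combination of CC-486 (5-azacitidine), romidepsin, lenalidomide and dexamethasone in patients with TCM". Section 1.1.1 words the primary objective as the safety, toxicity profile and MTD of lenalidomide "given as part of a four-drug combination treatment with romidepsin, CC-486 (5-azacitidine) and dexamethasone". Section 3.1 describes lenalidomide escalation "in combination with fixed doses of CC-486 (5-azacitidine), romidepsin (R) and dexamethasone (D) with an expansion cohort at the MTD", and Table 1 gives dexamethasone at the same dose on every dose level.

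Section 3.2 then requires that a DLT be "toxicity deemed related to lenalidomide, romidepsin and/or CC-486 (5-azacitidine) by the PI or designee". Dexamethasone is not on that list, and no reason is given. The opening sentence of section 3.1 and the MTD endpoint in section 10.1 also name only the three drugs. In section 10.4.2, adverse events are to be grouped "by relationship to study drug (e.g., lenalidomide, romidepsin", with CC-486 as the third example.

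Table 6 in section 3.5.1 covers treatment-related events. In its cycle 1 rows, any grade 4 event is marked as a DLT. So is a grade 3 event in the residual category that does not improve to grade 1 or better. Neither row names a causal drug. Section 8.1.5 asks for one judgement, related or not related to study product.

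**The concern.** The DLT count decides the MTD, and the MTD is a primary endpoint. If the question concerns four drugs but the count admits attribution to three, some severe toxicity of the regimen can fall outside the count because of the drug the investigator names.

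The category is not empty in principle. Section 14.4.2 lists dexamethasone toxicities, including raised blood sugar, mood change and muscle weakness. Hyperglycemia is not among the DLT exceptions in sections 3.2.1 and 3.2.2, so only the attribution clause would keep a grade 3 or higher event from counting. The study is open-label, and section 3.5 acknowledges that overlapping toxicity makes attribution to a single agent difficult.

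The rule is also one-sided. Sections 1.10 and 12.5.3 say dexamethasone was added to improve the tolerability of lenalidomide. Any such benefit lowers the DLT count, while toxicity attributed to dexamethasone alone cannot raise it.

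Small counts decide the outcome. Under section 3.3 and Table 3, one reclassified patient turns 0 of 3 into 1 of 3, which calls for more patients at that level. It turns 1 of 6 into 2 of 6, which is above the MTD criterion.

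**Working it through.** **Step 1: reproduce the plan's table.** Under Table 3, escalation follows 0 of 3 DLTs, or 1 of 3 followed by 0 of 3. For a true DLT rate p:

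P(escalate) = (1-p)³ + 3p(1-p)² × (1-p)³

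At p = 0.20: 0.512 + 0.384 × 0.512 = 0.709. At 10% to 60% the formula gives 0.906, 0.709, 0.494, 0.309, 0.172 and 0.082. Section 10.2 prints 0.91, 0.71, 0.49, 0.31, 0.17 and 0.08, so all six reproduce.

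**Step 2: what p measures.** These figures hold for the DLT rate as section 3.2 defines it. Let p3 be the rate of DLT-grade toxicity attributed to at least one of the three listed drugs, and d the rate attributed to dexamethasone alone. Taking the two as independent, the rate under four-drug attribution is

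t = 1 - (1-p3)(1-d)

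The documents give no value for d. The range of 2% to 15% is an assumption, as is independence.

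**Step 3: compare the rule as written with four-drug counting.** Example with p3 = 0.20 and d = 0.10: t = 1 - 0.80 × 0.90 = 0.28, and P(escalate) falls from 0.709 to 0.536.

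| p3 | As written | d = 2% | d = 5% | d = 10% | d = 15% |
|---|---|---|---|---|---|
| 10% | 0.906 | 0.875 | 0.824 | 0.730 | 0.632 |
| 20% | 0.709 | 0.674 | 0.622 | 0.536 | 0.454 |
| 30% | 0.494 | 0.466 | 0.425 | 0.360 | 0.301 |

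Across these cells the rule as written escalates about 3 to 27 percentage points more often than it would if dexamethasone-only events counted.

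**Step 4: set section 3.2 beside Table 6.** Take cycle 1 events attributed to dexamethasone alone.

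- Grade 4: not a DLT under section 3.2; a DLT under Table 6 if the event is regarded as treatment related.
- Grade 3 in the residual category, not improved to grade 1 or better: not a DLT under section 3.2; a DLT under Table 6 on the same reading.
- Grade 3 in the residual category that does improve: not a DLT under section 3.2; Table 6 does not label it.

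Table 6's title names three drugs as those to be modified, so its scope could be read as toxicity of those three. The text does not settle this.

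**The case against.** The strongest defence is that the exclusion is deliberate. The objective is the MTD of lenalidomide within the regimen, dexamethasone is fixed at every level including -1 and -2, and section 4.3 treats only the other three drugs as investigational. A dexamethasone-only event then says little about the lenalidomide dose. This does not settle the point. Romidepsin and CC-486 are also fixed across levels 1 to 4, and their toxicity counts. The documents never state the rationale.

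Several limits do stand.

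- A reader might infer that toxicity involving dexamethasone can never be a DLT. Joint attribution with a listed drug still counts, and section 8.1.5 requires only a reasonable possibility of causation. Most dexamethasone toxicities in section 14.4.2 have a counterpart among the listed drugs, so the affected set may be small.
- A reader might infer that such events vanish from the safety results. They do not: section 10.1 makes treatment-emergent event frequency a primary endpoint, section 8.2 records events whatever their relationship, and the list in section 10.4.2 is illustrative.
- The grade 3-4 hyperglycemia in Tables 5 and 5.1 might seem to size the effect. Those regimens are presented without dexamethasone and the tables are not limited to cycle 1, so they measure neither dexamethasone-only toxicity nor misattribution.
- Section 10.3.1 might seem to need the same edit. It sets when toxicity evaluability begins, not attribution.

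**Conclusion.** The inconsistency is real and should be resolved. Section 3.2 uses a narrower attribution set than the four-drug objective, and it can disagree with Table 6 on the same event. The exclusion can lower the DLT count on which the 20 mg MTD rests.

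The documents do not support the stronger conclusion that the MTD is biased, because they show no cycle 1 event data and no dexamethasone-only attributions. Nor do they show that the rule carries into the Arm 3 safety report: escalation is complete, and adverse events there are tabulated whether or not they are labelled DLTs.

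The size is illustrative only. With p3 = 20% and an assumed d of 2% to 15%, P(escalate) is 0.71 as written against 0.67 to 0.45 under four-drug counting. If d is close to zero, the effect is negligible. The formula, the table in section 10.2 and the planned sample size are unaffected.

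**What to change.** Reconcile section 3.2, Table 6, and the three-drug wording in sections 3.1 and 10.1 with the four-drug objective, so that a single attribution set applies throughout. Add dexamethasone to the example attribution list in section 10.4.2.

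Review the Arm 1 cycle 1 events of grade 3 or higher that were not attributed to the three listed drugs. Report by dose level, beside the declared MTD, how many would be DLTs under four-drug attribution after applying the exceptions in sections 3.2.1 and 3.2.2. If none changes, saying so supports the MTD; if any does, readers can see at which level.

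The cost is a few wording changes and a small re-review: section 3.4.1 puts enrollment at 20 when Arm 1 was fully accrued. Because section 8.1.5 records only related or not related, source notes may be needed to recover the drug named. The downside is that the MTD statement may become less favourable.
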